3.2.3 PK Endpoints

REN001 plasma concentrations will be measured at each study visit*. The following parameters will be calculated for subjects recruited under Protocol Version 1.0: C_{trough} , C_{max} , T_{max} and Area Under Curve (AUC)_τ. The REN001 plasma concentrations may be included in a population PK analysis which will be reported separately to the Clinical Study Report for this study. REN001 metabolite concentrations may also be analyzed and reported.

3.2.4 Exploratory Endpoints

For mtDNA and nDNA subjects:

- Change from baseline to end of treatment in bone mineral density (BMD), as measured by dual energy x-ray absorptiometry (DXA), in the following:
 - Lumbar spine (L1 to L4) BMD
 - Total hip BMD and the femoral neck BMD (in the non-dominant hip)
 - Total hip, lumbar spine, and femoral neck T-scores and Z-scores

For nDNA subjects:

- Absolute values and changes from baseline in:
 - Distance walked during the 12-Minute Walk Test (12MWT)*
 - Modified Fatigue Impact Scale (MFIS) total scores and sub-scale scores*
- Patient Global Impression of Severity (PGIS) scores for fatigue and muscle symptoms
- Brief Pain Inventory (BPI) pain severity and pain interference scores*

- Patient Reported Outcomes Measurement Information System (PROMIS) Short Form-Functional Assessment of Chronic Illness Therapy (FACIT) Fatigue 13a scores*
- 36-item Short Form Health Survey (SF-36) domain scores (7-day recall)*
- Work Productivity and Activity Impairment Questionnaire: Specific Health Problem (WPAI:SHP) scores*
- First 6-minute walk distance and last 6-minute walk distance*
- Phenotypic description questions*
- Patient Global Impression of Change (PGIC) scores (muscle and fatigue symptoms).

*collected up to Month 24 only

3.3 Justification of the Study Design

There are no specific regulatory guidelines for the design of studies in patients with PMM and no approved safe and effective treatments for the disease. The STRIDE study is designed to assess the efficacy and safety of REN001 in patients with PMM caused by mtDNA gene mutations treated over a 24-week period.

This long-term safety study is designed to evaluate the safety and tolerability of long-term treatment with REN001 in subjects with PMM. In addition, valuable data regarding PMM associated symptoms, exercise endurance, quality of life and work productivity will be captured. This study will also give the opportunity to evaluate the effects of REN001 on safety and tolerability, any effects of REN001 on other outcome measures, and on quality-of-life measures in PMM subjects with nDNA mutations.

This study will also generate data to support the evaluation of the PK profile of REN001 over time.

3.4 Termination or Suspension of Study

The study will be completed as planned unless one or more of the following criteria occur that require temporary suspension or early termination of the study:

- New information or other evaluation regarding the safety of REN001 that indicates a change in the known risk/benefit profile for the compound, such that the risk/benefit is no longer acceptable for subjects participating in the study.
- Occurrence of local or global events (e.g., pandemic) that would impact the safety of subjects in the study.
- A decision by the Sponsor to suspend or discontinue development of the drug for the PMM indication.

3.5 Termination or Suspension of Investigational Sites

A study site may be terminated prematurely or suspended if the site (including the Investigator) is found to be in significant violation of GCP, the protocol, or the contractual agreement, or is unable to ensure adequate performance of the study, or as otherwise permitted by the contractual agreement.

3.6 Conditions for Individual Subject Withdrawal from the Study

The primary reason for subject withdrawal from the study should be recorded in the electronic Case Report Form (eCRF). Individual subjects may be withdrawn from the study in the following circumstances:

- Concurrent enrolment in other clinical studies involving investigational products or enrolment in other types of clinical research judged not to be scientifically or medically compatible with this study.
- Use of a prohibited concomitant medication.
- Major protocol deviation e.g., the discovery after administration of the first dose of study drug that the subject failed to meet protocol entry criteria or did not adhere to protocol requirements, and continued participation poses an unacceptable risk to the subject's health or undermines the ability to achieve the objectives of the trial.
- Lost to follow-up. The subject does not return to the study centre and attempts to contact the subject are unsuccessful. Attempts to contact the subject must be documented.
- Evidence of pregnancy during the treatment period of the study.
- Clinically significant changes from baseline in ECG considered treatment-related including an increase from baseline to an absolute heart rate corrected QT interval using Fridericia's formula (QTcF) value of ≥ 500 millisecond (msec). Single ECGs should be repeated at 5-minute intervals 3 times to confirm any increased QT interval values. In the event of increased QTcF, the subject must be monitored until the value returns to below 500 msec.
- Clinically significant muscle injury including test abnormalities (e.g., CK) as defined in [Section 3.7.1](#).
- Clinically significant liver toxicity including test abnormalities (e.g., ALT/AST) as defined in [Section 3.7.2](#).
- Clinically significant kidney toxicity including test abnormalities (e.g., creatinine levels) as defined in [Section 3.7.3](#).
- A TEAE that could result in a significant impairment. Subjects should be followed with appropriate medical management until there is a return to normal or baseline values or a clinical diagnosis of an emergent illness is confirmed.
- Voluntary withdrawal. The subject wishes to discontinue study drug and withdraw from the study. Subjects may withdraw from the study at any time without penalty and for any reason without prejudice to their future medical care. In all cases, the reason(s) for withdrawal, including the primary reason, must be recorded in the eCRF. Note: All attempts should be made to determine the underlying reason for the withdrawal and, where possible, the primary underlying reason should be recorded (i.e., withdrawal due to an AE should not be recorded in the "voluntary withdrawal" category).

If a subject is prematurely withdrawn from the study drug, the Investigator must make every effort to perform the evaluations described for the Early Withdrawal visit and a further Follow-up contact approximately 30 days after the last dose of study drug (if required, see [Section 6.14](#)). If the subject is withdrawing consent for continuing in the study and/or further contact no further assessments will be performed.

3.7 Strategy for Potential Withdrawal due to Laboratory Test Abnormalities

[figure not shown]
3.7.1 Safety Monitoring for Muscle Injury

Patients with PMM often present with mild to moderate baseline elevations in CK and can experience transient episodes of significantly elevated CK induced by acute illness, vigorous exercise, and other conditions. These elevations are not associated with symptoms or signs and the patients are typically well. CK elevations are generally of the skeletal muscle

fraction. However, a small proportion of the total CK may be from the myocardial fraction reflecting a small amount of this fraction found in skeletal muscle rather than the presence of myocardial injury. Importantly, these elevations are entirely to be expected in this patient population with underlying muscle disease and are not synonymous with clinically significant rhabdomyolysis. Similarly, elevations in serum aminotransferases and uric acid can accompany CK elevations and may not be indicative of liver disease.

True, clinically significant, rhabdomyolysis may also occur in these patients and must be managed appropriately. Rhabdomyolysis is characterized by severe acute muscle injury resulting in muscle pain, weakness, and/or swelling with release of myofiber contents into the bloodstream. Symptoms develop over hours to days following a triggering event and may be associated with dark pigmentation of the urine ([Nance & Mammen, 2015](#)). Acute kidney injury is a complication of rhabdomyolysis. The risk of acute kidney injury is low in patients with CK levels less than 15,000 international units per liter (IU/L). The CK algorithm below has been designed to identify those subjects potentially at risk of true rhabdomyolysis and ensure appropriate early action is taken to monitor and treat the subjects accordingly.

Figure 2: CK Algorithm

For the purpose of the different enrollment options, baseline is considered the visit where the subject starts drug.

3.7.2 Safety Monitoring for Liver: Management and Stopping Rules

Subjects with clinically significant liver disease or impairment have been excluded. It would be inappropriate to exclude all subjects with milder elevations in LFTs out of the normal range because subjects with PMM can present with elevations in CK levels that are often accompanied by elevated LFTs (ALT and AST), which are not indicative of liver disease. Accordingly, these elevations appear to be transient and resolve spontaneously (Tarnopolsky 2016). Although serum ALT and AST values have shown good diagnostic accuracy in patients with chronic liver disease, AST and ALT levels can be increased immediately after muscular exertion as well (Lippi 2008).

In the event that a subject presents with raised LFTs during the study the following management guidelines and stopping rules should be followed:

- For subjects who enrol with a baseline below the ULN and present with an increase in serum ALT or AST > 3xULN, repeat testing of ALT, AST, ALP and total bilirubin will be obtained as soon as possible, ideally within 48-72 hours, to confirm the abnormality and whether the abnormality is increasing or decreasing.

- For subjects who enrol with a baseline above the ULN and present with an increase in serum ALT or AST > 3xULN and at least 2x their baseline value, repeat testing of ALT, AST, ALP and total bilirubin will be obtained as soon as possible, ideally within 48-72 hours, to confirm the abnormality and whether the abnormality is increasing or decreasing.
- If symptoms persist or repeat testing shows ALT > 3xULN for subjects with normal baseline measures or 2x their baseline value for subjects with elevated values at baseline, initiate close observation with repeat testing 2-3 times weekly, or as clinically mandated, to determine whether the abnormalities are improving or worsening (see below for further details).
- If close monitoring is not possible, as a precautionary measure study drug should be withheld and continued participation in the study should be discussed with the Medical Monitor.

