1.5 Dose Selection Rationale

The dose of 100mg once daily used in this study is the same dose used in the 2 feeder studies for mtDNA-PMM subjects: Study REN001-101 (a UK only study) and the STRIDE study.

To date a total of 163 subjects have been enrolled and 106 subjects received REN001 in four completed clinical trials pertinent to this indication (HPP593-101 (single dose, healthy volunteers); HPP593-102 (14-day, repeat dose study in obese moderately dyslipidemic subjects); HPP593-103, (28-day, healthy volunteer pharmacodynamic study in induced muscle atrophy); REN001-101 (up to 48 weeks, repeat dose in mtDNA-PMM subjects; treatment received for up to 40 weeks due to curtailment of study during the COVID-19 pandemic). In the single dose study, doses ranged from 25mg to 250mg, doses in the 14-day study ranged from 50mg to 200mg QD or 100mg BID, in the 28-day study the dose was 100mg BID and in the 48-week study the dose was 100mg QD. Overall, REN001 was considered safe and well tolerated in all four clinical studies. No treatment related SAEs were reported. No clinically significant abnormalities were observed in any safety parameters including vital signs, ECGs, and physical exams.

In Study REN001-101, most subjects with mtDNA-PMM who received REN001 at an oral dose of 100mg once daily for 12 weeks improved 12MWD, 30 second sit to stand, VO₂ max and gait analysis with these physical function measures being supported by the PRO data. PRO data also reported a reduction in muscle related symptoms and fatigue. Pharmacological activity of the REN001 at 100mg per day was also shown in Phase 1 studies in other indications (see Investigator Brochure for details).

The safety and the pharmacodynamic effects observed in these four completed studies support the 100mg QD dose level in the primary mitochondrial myopathy population evaluated in both the STRIDE study and in this long-term safety study. Although, there is no prior history of REN001 exposure in patients with nDNA mutations, the safety profile of REN001 in this population is not expected to differ significantly from patients with mtDNA mutations. nDNA-PMM patients enrolling in this study must meet similar screening safety

requirements as the naïve mtDNA-PMM patients who previously enrolled in the STRIDE study or in the REN001-101 study.

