3.7.2.2 Discontinuation – All Subjects

Discontinuation or interruption of study drug should be considered, in consultation with the Medical Monitor and the Sponsor where possible, if:

- ALT or AST > 8xULN.
- ALT or AST > 5xULN for more than 2 weeks.
- ALT or AST > 3xULN and total bilirubin > 2xULN or INR >1.5.
- ALT or AST > 3xULN with the appearance of fatigue, nausea, vomiting, right upper quadrant pain or tenderness, fever, rash, and/or eosinophilia (>5%).

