3.7.2.3 Discontinuation – Subjects in German sites

Discontinuation of study drug should occur and close monitoring continued, if:

- ALT or AST > 8xULN.
- ALT or AST > 5xULN for more than 2 weeks.
- ALT or AST > 3xULN and total bilirubin > 2xULN or INR >1.5.

- ALT or AST > 3xULN with the appearance of fatigue, nausea, vomiting, right upper quadrant pain or tenderness, fever, rash, and/or eosinophilia (>5%).

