4 STUDY POPULATION

Protocol inclusion and exclusion criteria in [Section 4.1](#) are intended for all subjects enrolling into the study. These are the only criteria to be assessed for mtDNA-PMM subjects enrolling at the STRIDE Week 24 or STRIDE FU visits. Additional eligibility criteria will need to be met for those mtDNA-PMM subjects enrolling after exiting from either of the 2 feeder studies and nDNA-PMM subjects ([Section 4.2](#)). In addition, nDNA-PMM subjects will have some screening data independently reviewed by the PSOC to confirm eligibility. nDNA-PMM subjects will not be enrolled in France.

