4.2 Additional Exclusion Criteria

Subjects with mtDNA-PMM enrolling after exiting from either of the 2 feeder studies and subjects who have nDNA-PMM will be required to fulfil these additional exclusion criteria:

1. Clinically significant kidney disease or impairment, with an eGFR less than 60ml/min/1.73m² using the CKD-EPI creatinine equation at baseline. German sites - see alternative criteria below in [Section 4.3](#).
2. Clinically significant liver disease or impairment with AST or ALT >2.5 x ULN, or Total bilirubin > 1.6 x ULN or >ULN with other signs and symptoms of hepatotoxicity at baseline. (Subjects with an isolated elevated bilirubin (e.g., < 2 x ULN) may be included after discussion with the Medical Monitor if the cause is due to a benign hereditary disorder of metabolism such as Gilbert's syndrome.)
3. Uncontrolled diabetes and/or a glycosylated hemoglobin (HbA1c) of $\geq 11\%$. German sites - see alternative criteria below in [Section 4.3](#).
4. Evidence of significant concomitant clinical disease that may need a change in management during the study or could interfere with the conduct or safety of this study. (Stable well-controlled chronic conditions such hypercholesterolemia, gastroesophageal reflux, or depression under control with medication, are acceptable provided the symptoms and medications would not be predicted to compromise safety or interfere with the tests and interpretations of this study.)
5. Clinically significant cardiac disease and/or clinically significant ECG abnormalities including a Baseline QTcF of ≥ 450 msec, 2nd degree heart block, symptomatic tachyarrhythmia or unstable arrhythmia that in the opinion of the Investigator should exclude the subject from study completion. Subjects with right bundle branch block, left fascicular block and long PR interval which are common in PMM may be enrolled if the Investigator considers that the condition would not compromise their safety in this study.
6. Treatment with an investigational drug, other than REN001, within 3 months or 5 drug half-lives, whichever is longer, prior to Day 1.
7. Have been hospitalized within the 3 months prior to Screening for any major medical condition (as deemed by the Principal Investigator).
8. Subjects with poor nutritional status as determined by the Investigator.

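### With a baseline ALT/AST above 2.5xULN, a value above 5xULN but below twice baseline has no mandated repeat, so the two-week stopping criterion may be recognised only at the next scheduled chemistry

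*Protocol*

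**What the plan says.** **Repeat testing (Protocol 3.7.2).** A subject with a normal baseline is retested once ALT or AST passes 3xULN, ideally within 48-72 hours. A subject with a raised baseline is retested only if they "present with an increase in serum ALT or AST > 3xULN and at least 2x their baseline value".

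**Close observation (3.7.2).** Testing two to three times weekly starts as follows: "If symptoms persist or repeat testing shows ALT > 3xULN for subjects with normal baseline measures or 2x their baseline value", the last limb being for subjects with raised baselines. This step names ALT only.

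**Stopping criteria (3.7.2.2, 3.7.2.3).** All are multiples of ULN with no reference to baseline. One needs time to pass: "ALT or AST > 5xULN for more than 2 weeks". The others can be met on one occasion: >8xULN, or >3xULN with raised bilirubin or INR, or >3xULN with listed symptoms or eosinophilia. Under 3.7.2.2 discontinuation or interruption is to be considered. For German sites 3.7.2.3 is firmer: "Discontinuation of study drug should occur and close monitoring continued, if".

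**Baseline.** The note under the CK figure in 3.7.1 reads: "For the purpose of the different enrollment options, baseline is considered the visit where the subject starts drug".

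**Entry limits.** Of the criteria in 4.1, Section 4 says: "These are the only criteria to be assessed for mtDNA-PMM subjects enrolling at the STRIDE Week 24 or STRIDE FU visits". The numeric ALT/AST limit, "Clinically significant liver disease or impairment with AST or ALT >2.5 x ULN", is in 4.2, which covers subjects enrolling after leaving a feeder study and nDNA-PMM subjects.

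**The concern.** The retest rule scales with baseline, but the two-week criterion does not. A subject with a normal baseline and an ALT of 5.5xULN is retested within days. A subject with a baseline of 3xULN and the same ALT is not, because 5.5 is below twice baseline. Yet the criterion of more than two weeks above 5xULN applies equally to both, and it cannot be established from one sample.

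Long-term safety is the primary objective. Most mtDNA-PMM subjects are expected to roll over at STRIDE Week 24, some of them from blinded REN001. If baseline is the enrolment-visit value, a rise that developed during STRIDE becomes the reference that must double before a retest is required. What is at stake is a delay of weeks to months in recognising that a stopping criterion has been met, in subjects whose enzymes are already raised.

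**Working it through.** The plan gives no figure of its own to reproduce. The check applies the visible rules to a range of baselines and then measures the time to the next scheduled chemistry.

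**Step 1: where the retest starts.** With baseline B (in xULN) above 1, a value must exceed 3 and be at least 2B, so the trigger is T(B) = max(3, 2B).

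**Step 2: values that count towards the two-week criterion without a mandated repeat.** The value must exceed 5, lie above baseline (3.7.2 speaks of an increase), be below 2B, and not exceed 8, since >8xULN is a criterion on its own. The range runs from max(5, B) to min(2B, 8). For B up to 5 it is non-empty only if 2B > 5, that is B > 2.5.

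| B (xULN) | Repeat mandated from | Above 5xULN, no mandated repeat |
|---|---|---|
| 2.5 | 5 | none |
| 2.6 | 5.2 | 5 to 5.2 |
| 3 | 6 | 5 to 6 |
| 3.5 | 7 | 5 to 7 |
| 4 | 8 | 5 to 8 |
| 4.5 | 9 | 5 to 8 |
| 5 | 10 | 5 to 8 |
| 6 | 12 | 6 to 8 |

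For B above 4 the retest trigger lies above the >8xULN stopping criterion itself (B=4.5: 9 against 8).

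**Step 3: the close-observation step.** Take B=3. A first value of 6.2 is repeated, because 6.2 ≥ 6. A repeat of 5.8 is below 6 and does not open close observation, although it is still above 5. A rise in AST alone does not open it either, as the step is worded.

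**Step 4: time to the next scheduled chemistry.** Days and windows are from Protocol Table 3: 28 (±3), 84 (±7), 168 (±7), then 336, 504, 672, 840, 1008, 1176 and 1344 (each ±21). Germany adds 252 and 420 (±21). Shortest gap = (next day − its window) − (this day + its window); the longest gap reverses the signs.

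- Month 1 to 3: 77 − 31 = 46; 91 − 25 = 66 days.
- Month 3 to 6: 161 − 91 = 70; 175 − 77 = 98.
- Month 6 to 12: 315 − 175 = 140; 357 − 161 = 196.
- Month 12 to 18 and each later interval: 483 − 357 = 126; 525 − 315 = 210.
- Germany, Month 6 to 9: 231 − 175 = 56; 273 − 161 = 112.
- Germany, Month 9 to 12, 12 to 15 and 15 to 18: for the first, 315 − 273 = 42 and 357 − 231 = 126; the other two are the same.

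Counting from the first post-baseline value, every gap exceeds 14 days.

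**Step 5: who can have B above 2.5.** Week 24 and follow-up roll-overs meet no numeric ALT/AST limit at entry. It is less likely after a feeder-study exit or in nDNA-PMM subjects, where 4.2 applies. It is not impossible there: the criterion is tied to clinically significant liver disease or impairment, and chemistry is drawn again at the first-dose visit (6.1.3.2, 6.1.4.2). German roll-overs are unclear: Protocol 4.3 replaces criteria 1, 3 and 9 but not the liver criterion, while SAP 3.3 says all German subjects face additional eligibility checks.

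**The case against.** The strongest reply is that the roll-over group does not go unwatched.

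- Exclusion 6 in 4.1.2 lets the investigator and Medical Monitor keep out anyone with a laboratory abnormality that raises risk.
- Section 1.5 says nDNA-PMM subjects "must meet similar screening safety" requirements to those mtDNA-PMM subjects met on entering STRIDE or REN001-101. A baseline above 2.5xULN would therefore generally need a rise during STRIDE.
- The STRIDE schedule (SAP Appendix 2, footnote 11) asks that clinically significant Week 24 abnormalities be followed to resolution, and STRIDE adverse events still ongoing are carried over and followed (7.1.1.3).
- The Medical Monitor and site physicians review data as they arrive (1.4.3), repeats and unscheduled visits are allowed (7.1.2, 6.15), and persisting symptoms can open close observation.
- The stopping criteria are not conditional on the retest rule. An investigator who sees 5.5xULN and knows the two-week criterion would have reason to resample.

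All of this stands, and it narrows the point. It does not close it: none of these provisions sets a retest interval for an isolated, asymptomatic value, and 3.7.2.2 says when to consider stopping, not when to resample. Sections 3.7.1 and 3.7.2 also tell sites that raised aminotransferases in PMM may not mean liver disease, so such a value may not be classed as an adverse event.

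A baseline-relative rule is also a deliberate and reasonable choice in this disease. That is accepted; the point concerns only the second sample that the two-week criterion needs.

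**Conclusion.** The point holds for the visible text of 3.7.2, as a targeted clarification worth considering. For B above 2.5, an asymptomatic, normal-bilirubin value in the ranges of Step 2 has no mandated repeat. The two-week criterion may then be recognised only at the next scheduled chemistry, 46 to 210 days later (Germany 42 to 126 days from Month 6 to Month 18).

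This rests on two assumptions. B is taken as the enrolment-visit value, which fits the wording of 3.7.2 and the note in 3.7.1. It is also assumed that nothing in the CK algorithm (Figure 2) or the STRIDE liver rules, neither of which is visible, forces an earlier ALT/AST retest. The number affected cannot be estimated and may be small.

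A reader might infer more than the documents support:

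- *That such elevations would go undetected.* Two consecutive scheduled values would show them, and >8xULN, or >3xULN with raised bilirubin or listed symptoms, needs no two-week wait.
- *That roll-overs enter with no liver safeguard.* Exclusion 6 and the STRIDE follow-up apply, though by clinical discretion.
- *That the whole 5-8xULN band is uncovered at any high baseline.* For B above 5, values at or below B are not an increase.
- *That INR must be added because Table 4 omits it.* It is an alternative to bilirubin, which is measured routinely, and 3.7.2.1 already provides for it as appropriate.

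**What to change.** Amend Protocol 3.7.2 in three places:

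1. Raised-baseline retest trigger: ALT or AST >3xULN and at least 2x baseline, OR >5xULN and above baseline.
2. If the repeat confirms >5xULN, require a further ALT/AST test just after 14 days, whether or not the value reaches twice baseline.
3. Close-observation entry: change ALT to ALT or AST.

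With the first change, every value above max(5, B) is retested, so the range in Step 2 is empty at every baseline. The second covers the Step 3 case, where a repeat of 5.8xULN at B=3 currently leads nowhere. The words *and above baseline* avoid a retest at every visit for a stable muscle-origin elevation that already exceeds 5xULN.

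The cost is protocol wording, a memo to sites and a few extra blood draws, some of them for elevations that prove to be of muscle origin.

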3.7.2.1 Guidelines for Close Observation

- Repeated ALT, AST, ALP, and total bilirubin tests two or three times weekly.
- Frequency of re-testing can decrease to once a week or less if abnormalities stabilize or the study drug has been discontinued and the subject is asymptomatic.
- Obtain a more detailed history of symptoms and prior or concurrent diseases.
- Recheck history of concomitant drug use (including non-prescription medications and herbal and dietary supplement preparations), alcohol use, recreational drug use, and any special diets.
- Rule out acute viral hepatitis types A, B, C, D, and E; autoimmune or alcoholic hepatitis; Non-alcoholic steatohepatitis (NASH); hypoxic/ischemic hepatopathy; and biliary tract disease.
- Obtain a history of exposure to environmental chemical agents.
- Obtain additional tests to evaluate liver function, as appropriate (e.g., International normalized ratio (INR) or Prothrombin time (PT), direct bilirubin).
- Consider gastroenterology or hepatology consultations.

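### Close liver observation (Protocol 3.7.2) is triggered by ALT only, although the retest steps before it and every discontinuation criterion after it use ALT or AST

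*Protocol*

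**What the plan says.** Protocol 3.7.2 sets out a sequence.

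- **Retest.** For subjects with baseline below the ULN, the repeat panel applies when they "present with an increase in serum ALT or AST > 3xULN, repeat testing" being due ideally within 48-72 hours. For those with raised baseline, the trigger is again either enzyme above 3xULN, plus at least twice baseline.
- **Close observation.** The next bullet reads "If symptoms persist or repeat testing shows ALT > 3xULN for subjects with normal baseline measures or 2x their baseline value" (the latter for subjects with elevated baselines), then "initiate close observation with repeat testing 2-3 times weekly, or as clinically mandated".
- **Fallback.** "If close monitoring is not possible, as a precautionary measure study drug should be withheld".

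Protocol 3.7.2.1 describes close observation. ALT, AST, ALP and total bilirubin are all repeated, and "Frequency of re-testing can decrease to once a week or less if abnormalities stabilize or the study drug has been discontinued". It also asks sites to "Obtain additional tests to evaluate liver function, as appropriate (e.g., International normalized ratio (INR) or Prothrombin time (PT), direct bilirubin".

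Protocol 3.7.2.2 then lists four criteria for considering discontinuation or interruption, among them "ALT or AST > 5xULN for more than 2 weeks". Section 3.7.2.3 repeats the four for German sites, where meeting one is a direction to discontinue and to carry on close monitoring.

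**The concern.** AST counts when a rise is first found and when stopping is decided, but not at the step that generates the data between the two. Read literally, a subject with no symptoms whose repeat test shows raised AST and ALT below the trigger leaves the algorithm after one retest.

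The two-week criterion suffers most. It cannot be judged from the first value and a repeat two or three days later; it needs a value beyond day 14. In Germany this criterion is a stop. Elsewhere it prompts a decision, with interruption also open (3.7.2.2, 3.9). The German wording also presumes that close monitoring is already under way.

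There is a smaller knock-on effect. INR is part of the third criterion but is not in the Table 4 laboratory list. It is named as a test only in the close-observation guidance, so a subject who never enters close observation is not prompted for it.

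**Working it through.** **Step 1: the enzyme named at each step.**

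| Step | Section | Enzyme |
|---|---|---|
| Retest, baseline below ULN | 3.7.2 | ALT or AST |
| Retest, baseline above ULN | 3.7.2 | ALT or AST |
| Start close observation | 3.7.2 | ALT only (or persisting symptoms) |
| Tests within close observation | 3.7.2.1 | ALT and AST |
| Four discontinuation criteria | 3.7.2.2 | ALT or AST in 4 of 4 |
| Four criteria, Germany | 3.7.2.3 | ALT or AST in 4 of 4 |

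**Step 2: is there a stated reason?** None was found. Section 3.7.2 says "AST and ALT levels can be increased immediately after muscular exertion as well", and 3.7.1 speaks of aminotransferases together when describing rises that accompany CK. Neither separates AST from ALT.

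**Step 3: what else would bring the subject back?** Data review by the Medical Monitor and site physicians (1.4.3) has no retest interval. AE follow-up (7.1.1.8.2) applies only if the change is judged clinically significant (7.1.1.2), and it has no interval either. Unscheduled visits (6.15) are discretionary. The CK algorithm (Figure 2 in 3.7.1) may contain retests, but the figure was not available and was not assessed. That leaves the scheduled bloods.

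**Step 4: nominal gaps between scheduled bloods** (target days from Protocol Table 3).

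- Baseline to Month 1: 28 − 1 = 27 days, but the baseline sample is not an on-treatment value in this study.
- Month 1 to 3: 84 − 28 = 56
- Month 3 to 6: 168 − 84 = 84
- Month 6 to 12: 336 − 168 = 168
- Month 12 to 18: 504 − 336 = 168
- Germany, Month 6 to 18: 252 − 168 = 336 − 252 = 420 − 336 = 504 − 420 = 84

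**Step 5: shortest possible gaps.** Take the first visit as late and the next as early as the windows allow (±3 days at Month 1, ±7 at Months 3 and 6, ±21 later).

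- Month 1 to 3: (84 − 7) − (28 + 3) = 46
- Month 3 to 6: 161 − 91 = 70
- Month 6 to 12: 315 − 175 = 140
- Month 12 to 18: 483 − 357 = 126
- Germany, Month 6 to 9: 231 − 175 = 56
- Germany, Month 9 to 12: 315 − 273 = 42
- Germany, Month 12 to 15: 399 − 357 = 42
- Germany, Month 15 to 18: 483 − 441 = 42

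The minimum is 46 days, or 42 in Germany. Against the 14-day criterion, 46/14 = 3.3 and 42/14 = 3.0.

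**Step 6: time past the 14-day point.** Suppose a rise is found at a scheduled blood and nothing is ordered beyond the 48-72 hour repeat. The next scheduled value then falls nominally 56 − 14 = 42 to 168 − 14 = 154 days after the two-week mark, and at the least 42 − 14 = 28 days after it.

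**Step 7: with AST in the trigger.** Two to three tests a week give at most 3 × 2 = 6 tests in the two weeks, so the criterion could be assessed on time.

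**The case against.** Several points can fairly be made for the plan.

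- **The raised-baseline limb is less clear-cut.** It refers to twice the baseline value without naming an enzyme again, and could be read as whichever enzyme rose. The gap is plainest for subjects with normal baseline. The more natural reading still carries ALT forward, and the same edit settles both limbs.
- **The intent is visible.** Section 3.6 refers to ALT/AST together, and a physician who has confirmed a high AST cannot apply the two-week rule without testing again. That is true of good practice, but the text sets no interval.
- **Symptoms also trigger close observation.** Symptoms are not defined, and many subjects with this disease have fatigue or muscle pain. This narrows the group without removing it.
- **The waiting times are conditional.** They assume that nobody orders another test. They describe the schedule, not expected care. This stands, and the unseen CK algorithm could shorten them.
- **INR would not become mandatory.** Even under close observation it is done as appropriate. This stands: the edit prompts INR but does not require it.
- **ALT only may have been deliberate, because AST is often muscular.** No section says so, and AST would then hardly appear in every stopping criterion.
- **The change is a protocol amendment.** Section 9.9 requires a written amendment, with ethics and authority approval where appropriate. This stands as a cost.

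**Conclusion.** The concern holds. As written, the protocol does not require the serial AST values that its own two-week criterion needs. The shortest scheduled gap on treatment is about three times the length of the criterion.

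The affected group is narrow: AST above 5x and up to 8xULN, ALT below the trigger, no symptoms, and no bilirubin or INR criterion met. The documents do not say how often AST rises alone, so the number of subjects is not estimated. No effect on the primary endpoint is claimed.

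The conclusion rests on a literal reading of the close-observation bullet and on the safeguards that could be read, which exclude the CK figure. The text comparison is certain. The practical consequence depends on how far sites and the Medical Monitor retest on their own initiative. It should be corrected because it concerns a stopping rule for participant safety and the correction is small.

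**What to change.** In the close-observation bullet of 3.7.2, insert two words so that the repeat-test trigger names ALT or AST above 3xULN. Leave the rest of the bullet as it is, including the latitude to test as clinically mandated. If ALT alone was intended, state the reason and say how the two-week criterion is to be applied to AST.

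The cost is an amendment under section 9.9, with approvals where appropriate, and a clarification letter to sites. Some subjects whose AST rise proves muscular would have extra tests (up to six in two weeks, then weekly or less once values are stable) and the 3.7.2.1 work-up. Where close monitoring is not possible, the precautionary withholding of drug would extend to them as well.
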